### 1.3 RATIONALE

Acquired resistance to enzalutamide monotherapy limits the durability of response in both the first line and second line treatment setting. (61) Dual targeting of the AR and HIF-1 $\alpha$  axis represents a novel therapeutic approach for CRPC treatment, with the inhibition of HIF-1 $\alpha$  as a possible mechanism for overcoming enzalutamide resistance and potentiating anti-androgen/AR therapy. (32, 46) The treatment combination of enzalutamide and CRLX101, a HIF-1 $\alpha$  inhibitor, is aimed to reduce cross-talk of both androgen receptor and HIF-1 $\alpha$  signaling pathways, reverse enzalutamide resistance and increase time to progression. To test this concept, this pilot study will examine the efficacy of combination therapy to determine if further investigation is warranted.

## 2 ELIGIBILITY ASSESSMENT AND ENROLLMENT

## 2.1 ELIGIBILITY CRITERIA

## 2.1.1 Inclusion Criteria

2.1.1.1 Patients must have histologically or cytologically confirmed prostate cancer confirmed by either the Laboratory of Pathology at the NIH Clinical Center or Walter Reed National Military Medical Center at Bethesda prior to starting this study. If no pathological specimen is available, patients may enroll with a pathologist's report showing a histological diagnosis of prostate cancer and clinical course consistent with the disease.

- 2.1.1.2 Patients must have progressive mCRPC. There must be radiographic evidence of disease progression or biochemically (rising PSA levels on successive measurements) recurring disease despite adequate testosterone suppression.
- 2.1.1.3 Progression must be evidenced and documented by any of the following parameters:
  - PSA progression defined by a minimum of two rising PSA levels with an interval of ≥1 week between each determination
  - Appearance of one or more new lesions consistent with prostate cancer on bone scan
  - New or growing lesions on CT scan
- 2.1.1.4 Patients must have metastatic disease, per RECIST 1.1(62). See Section 6.3 for the evaluation of measurable disease.
- 2.1.1.5 Patients must have received treatment with prior enzalutamide for two or more cycles and must have had evidence of disease progression while on enzalutamide.
- 2.1.1.6 Patients who have received antiandrogens such as flutamide, bicalutamide, or nilutamide for >6 months immediately before enrollment on this study must be off treatment for 4 weeks (6 weeks for bicalutamide) and demonstrate a continued rise in PSA. Patients on antiandrogens for <6 months must be off medication for 2 weeks.

- 2.1.1.7 Age ≥18 years. Because no dosing or adverse event data are currently available on the use of enzalutamide and CRLX101 in patients <18 years of age and prostate cancer is not common in children <18 years of age, children are excluded from this study.
- 2.1.1.8 Patients must have adequate organ and marrow function as defined below:

 
leukocytes
 
	≥3,000/mcL
- absolute neutrophil count	≥1,500/mcL
– platelets	≥100,000/mcL

 
total bilirubin
 
patients with Gilbert's syndi
 
	within normal institutional limits; for come, total bilirubin ≤3.0 mg/dL
– hemoglobin	$\geq 9 \text{ g/dL}$
- serum albumin	$\geq$ 2.8 g/dL
- AST(SGOT)/ALT(SGPT)	< 2.5 X institutional upper limit of normal
	(<5 X institutional ULN for liver metastases)
- creatinine	within 1.5X normal institutional limits
	OR

 
creatinine clearance
 
	$\geq$ 60 mL/min/1.73 m  for patients with creatinine levels above institutional normal.

- 2.1.1.9 Patients must have castrate levels of testosterone (<50 ng/dL [1.74 nmol/L]).
- 2.1.1.10 Patients must have undergone bilateral surgical castration or must continue on GnRH agonists/antagonists for the duration of the study.
- 2.1.1.11 Patients on 5-alpha reductase inhibitors such as finasteride or dutasteride must stop medication at least 28 days prior to study entry.
- 2.1.1.12 The effects of enzalutamide and CRLX101 on the developing human fetus are unknown. For this reason and because androgen receptor antagonists and topoisomerase I inhibitors as well as other therapeutic agents used in this trial are known to be teratogenic, all study subjects must agree to use a condom during the study treatment period and for 120 days following the last dose of study drug. Should a woman become pregnant or suspect she is pregnant while her partner is participating in this study, she should inform her treating physician immediately.
- 2.1.1.13 ECOG performance status  $\leq 2$  (Karnofsky  $\geq 60\%$ , see **APPENDIX A**).
- 2.1.1.14 Ability of subject to understand and the willingness to sign a written informed consent document.
- 2.1.2 Exclusion Criteria
- 2.1.2.1 Patients who are receiving any other investigational agents. A minimum washout period of 28 days is required prior to the initiation of on study treatment, unless the patient is receiving immunotherapy, for which the minimum washout period will be 14 days. This is because Immune-related toxicities are distinct and unlikely to synergize with this protocol therapy, a shorter washout period is reasonable and customary in clinical trials.
- 2.1.2.2 Patients who have been treated with prior secondary hormonal manipulations with proposed investigational rationale for having efficacy against AR-V7 splice variants. This includes but is not limited to EPI-002 and AZD5312. (Note: patients previously treated with abiraterone, orteronel (TAK-700), apalutamide (ARN-509), galeterone, or VT-464 will be eligible for this study. Patients who have received prior chemotherapy will also be eligible for this study).
- 2.1.2.3 Patients with known brain metastases should be excluded from this clinical trial because of their poor prognosis and because they often develop progressive neurologic dysfunction that would confound the evaluation of neurologic and other adverse events.
- 2.1.2.4 Patients with a recent (within 1 year) history of seizure or any condition that, in the opinion of the investigator, significantly increases seizure risk. Also current or prior treatment with anti-epileptic medications for the treatment of seizures. Transient ischemic attack within 12 months prior to study enrollment will not be permitted.
- 2.1.2.5 History of allergic reactions attributed to compounds of similar chemical or biologic composition to enzalutamide, CRLX101, or other agents used in study.
- 2.1.2.6 Patients with a history within the last 3 years of another invasive malignancy (localized non-melanoma skin and bladder cancers are allowed).
- 2.1.2.7 Uncontrolled intercurrent illness including, but not limited to, ongoing or active infection, symptomatic congestive heart failure, unstable angina pectoris, cardiac

arrhythmia, uncontrolled hypertension (SBP>170/DBP>105), or psychiatric illness/social situations within 6 months that would limit compliance with study requirements.

- 2.1.2.8 Patients who have received palliative radiotherapy within 2 weeks of study entry and have not recovered to Grade 1 or baseline from associated toxicities. Note: Patients may receive palliative radiation once enrolled on study, as per guidance outline in Section **4.2.2**. The subject has not recovered to baseline or CTCAE  $\leq$  Grade 1 from toxicity due to all prior therapies, including surgery, except alopecia and other non-clinically significant AEs.
- 2.1.2.9 Patients who are unable to swallow tablets or have a gastrointestinal disease that could hinder the absorption of enzalutamide
- 2.1.2.10 The use of any herbal products that may lower PSA levels (e.g. saw palmetto).
- 2.1.2.11 Patients with microscopic hematuria (defined as >100 RBCs on urinalysis) or worsening urinary symptoms within 7 days prior to the initiation of study treatment.
- 2.1.2.12 Known HIV-positive patients on antiretroviral therapy are ineligible because of potential pharmacokinetic interactions with study drugs. However, patients with long-standing (>5 years) HIV on antiretroviral therapy >1 month (undetectable HIV viral load and CD4 count > 150 cells/ $\mu$ L) may be eligible if the Principal Investigator or designee determines no anticipated clinically significant drug-drug interactions.
- 2.1.3 Inclusion of Minorities and Women

Men of all races and ethnic groups are eligible for this trial. Women are excluded as prostate cancer does not exist in this population.

2.1.4 Recruitment Strategies

This study will be listed on available websites (e.g. www.clinicaltrials.gov) and on NIH social media forums. Additionally, participants will be recruited from the current patient population at NIH.

2.2 SCREENING EVALUATION

Note: screening evaluation testing/procedures are conducted under the separate screening protocol, 01-C-0129 (Eligibility Screening and Tissue Procurement for the NIH Intramural Research Program Clinical Protocols).

The following tests may be obtained any time prior to enrollment:

• Pathological confirmation of diagnosis and PSA expression in either the Laboratory of Pathology at NIH Clinical Center, Walter Reed National Military Medical Center at Bethesda. However, if no pathologic specimen is available, participants may enroll with a pathologist's report showing a histologic diagnosis of prostate cancer and a clinical course consistent with the disease.

The following parameters will be obtained within 30 days prior to enrollment (unless otherwise noted):

- Tc-99 whole body scintigraphy
- CT of chest/abdomen /pelvis (MRI may be substituted at investigator's discretion).
- History and physical examination with ECOG and vital signs
- Serum PSA
- Complete blood count plus differential and platelet count
- Hepatic and Acute Care panels
- Testosterone level
- Urinalysis
- EKG
- 2.3 PARTICIPANT REGISTRATION AND STATUS UPDATE PROCEDURES

Registration and status updates (e.g. when a participant is taken off protocol therapy and when a participant is taken off-study) will take place per CCR SOP ADCR-2, CCR Participant Registration & Status Updates found here.

## 2.3.1 Treatment Assignment Procedures

## 2.3.1.1 Cohorts

Number	Name	Description
1	Lead-in Cohort	First 3-6 participants with metastatic castration resistant prostate cancer receiving escalating doses of CRLX101
2	Combination Treatment Cohort	Up to 21 participants with metastatic castration resistant prostate cancer receiving tolerable dose of CRLX101

### 2.3.1.2 Arms

Number	Name	Description
1	Lead-in safety	Combination treatment of increasing dose of CRLX101 with enzalutamide
2	Efficacy	Tolerable dose of CRLX101 in combination with enzalutamide (8 participants, expandable to 21 total participants)

## 2.3.1.3 Arm Assignment

Participants in cohort 1 will be directly assigned to arm 1 based on enrollment time in the study.

Participants in cohort 2 enrolled after the lead-in study will be directly assigned to arm 2.

## 2.4 BASELINE EVALUATION

The following parameters will be obtained within 14 days prior to start of treatment (unless otherwise noted):

2.4.1 Clinical Evaluation

• History and physical examination

- ECOG performance status
- Height, Weight
- Baseline EKG

## 2.4.2 Laboratory studies

- Complete blood count plus differential and platelet count
- Acute care panel
- Hepatic panel
- Mineral panel
- LDH, CK, Uric Acid, Total Protein
- Urinalysis within 7 days prior to treatment
- Serum PSA
- Activated partial thromboplastin time (APTT) and International normalized ratio (INR)

### 3.1.1 Lead-In Component

[figure not shown]

Figure 6: Lead-In Dosing Schema and DLT Assessment

For the first 3 to 6 participants, there will be a lead-in period of two cycles to ensure the safety and tolerability of CRLX101 in combination with enzalutamide. CRLX101 will be started at a dose of 12 mg/m^2, administered via IV infusion on Day 1. Enzalutamide will be administered orally at a dose of 160 mg once daily starting on Day 2 (C1D2) once the 24-hour pharmacokinetic sample timepoint has been collected (at least 24 hours after the end of the CRLX101 infusion). After the first dose on C1D2, Enzalutamide will be taken once daily for the full duration of the study. Participants will receive CRLX101 12 mg/m^2 via IV infusion on Cycle 1 Day 15 (C1D15), Cycle 2 Day 1 (C2D1), and Cycle 2 Day 15 (C2D15). On Cycle 3 Day 1 (C3D1), and Cycle 3 Day 15 (C3D15), CRLX101 will be administered at the previously established MTD (15 mg/m^2 administered via IV infusion). Participants will be assessed from Day 1 to Day 56 (C1D1 to C2D28) for dose limiting toxicities of the CRLX101 12 mg/m^2 dose and from Day 57 to 84 (C3D1 to C3D28) for dose limiting toxicities of the CRLX101 15 mg/m^2 dose (Enzalutamide will be at approximate steady state concentration following Day 29 [C2D1]). Following the DLT assessment period (at the start of Cycle 4), each participant will continue to receive CRLX101 at the participant's specific maximum tolerated dose via IV infusion every 2 weeks (Days 1 and 15) for every subsequent cycle.

For the purposes of this study, re-assessment of the CRLX101 RP2D will be determined based on DLTs deemed likely attributable to CRLX101. DLTs are outlined in Section **3.1.1.1** and the dose modification procedures of CRLX101 are outlined in **3.3.2**. Adverse events deemed attributable to enzalutamide will not influence the on-trial treatment of subsequent participants and will be managed according to the dose modification protocol outlined in Section **3.3.3**. Final determination of the drug attributable to an adverse event is at the discretion of the Principal Investigator or designee.

If none of the three participants experience a dose limiting toxicity during the lead-in phase (Day 1-84), subsequent participants enrolled on trial with receive CRLX101 at a dose of 15 mg/m^2 via IV infusion every 2 weeks.

If one of three participants experience intolerable toxicity during the lead-in phase, an additional 3 participants will be enrolled with no adjustments to the lead-in dosing schema. If no further toxicity is observed (or a total of 1 in 6 participants experience dose-limiting toxicity),

subsequent participants enrolled on study will receive CRLX101 at a dose of 15 mg/m^2 every 2 weeks. If 2 of 6 participants experience a dose limiting toxicity, the dose at which the DLT occurred will determine further action:

- If both participants experience a DLT attributable to CRLX101 at a dose of 15 mg/m^2 or only one participant experiences a DLT at 12 mg/m^2, subsequent participants will receive CRLX101 at 12 mg/m^2 every 2 weeks.
- If both participants experience a DLT attributable to CRLX101 at a dose of 12 mg/m^2, participants will be given one dose of CRLX101 at 9 mg/m^2.
  - If further toxicity is observed with the 9 mg/m^2 dose, an amendment to modify dosing strategies will be considered. If necessary, the RP2D will be determined at the discretion of the Principal Investigator or designee after factoring in participant specific characteristics and the nature of the adverse event.

[figure not shown]
Based on limited potential for overlapping toxicity and well-characterized pharmacokinetics for both enzalutamide and CRLX101, it is anticipated 3 participants will participate in the lead-in phase. An accrual ceiling of 6 participants for the lead-in phase will be used to account for possible dose adjustments based on DLTs.

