# 3.1.1.1 Dose Limiting Toxicity

Dose-limiting toxicity (DLT) is defined as an adverse event that is related (possibly, probably, or definitely) to the administration of CRLX101. DLTs (toxicities occurring within the first 84 days of treatment after the first intravenous infusion of CRLX101) will be defined using the National Cancer Institute (NCI) Common Terminology Criteria for Adverse Events (CTCAE) version 5.0. The following events will be considered DLTs if deemed drug-related:

- Grade ≥3 neutropenia complicated by fever ≥38.5°C (i.e. febrile neutropenia and/or documented infection.
- Grade 4 neutropenia that does not improve within 5 days \*
- Grade 4 thrombocytopenia that does not resolve within 5 days\* or any grade 3-4 thrombocytopenia complicated with hemorrhage;
- Grade 4 anemia that does not resolve within 7 days despite optimal therapy (withholding study drug and red blood cell transfusion);
- Any grade 3-4 non-hematologic toxicity (except fatigue/asthenia < 2 weeks in duration; mucositis in subjects who have not received optimal therapy for mucositis; vomiting or diarrhea lasts less than 72 hours whether treated with an optimal anti-emetic or anti-diarrheal regimen or not; or alkaline phosphatase changes)
- Failure to receive at least 75% of study drug doses during cycle 1 due to toxicity.
- Laboratory results of 3xULN elevation of transaminases and concomitant 2xULN total bilirubin without an alternative etiology
- Any toxicity resulting in greater than two weeks of dose delay.

\*Note: In the event of a Grade 4 neutropenia or thrombocytopenia, a full blood count must be performed no more than 5 days after the onset of the event to determine if a DLT has occurred. The subject will be closely monitored until the resolution to Grade 3 or less.

[figure not shown]

Figure 7: Dosing schema following the lead-in component.

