### 3.3 Dose Modifications

- 3.3.1 General Rules for Dosing Delays/Dose Modifications and Management of Toxicities
  - In the case of toxicity, appropriate medical treatment should be used (including antiemetics, anti-diarrheals, etc.).
  - Once a participant has a dose reduction for toxicity, the dose will not be increased.
  - A maximum of two dose reductions are permitted
  - If either agent is discontinued due to toxicity, the participant may continue on the other agent.
  - Participants continuing to experience toxicity at the off-treatment visit will be contacted for additional assessments until the toxicity has resolved or is deemed irreversible. When logistically feasible, willing participants will remain on the study to have additional assessments.
  - For AEs that are unrelated to the study drugs, dose may be held for up to 28 days at the discretion of the Principal Investigator or designee.
  - The associate investigator and/or PI will determine whether one or both drugs are responsible for an observed toxicity and will manage that toxicity as described below.

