3.3.2.2 CRLX101-Related Hematologic Toxicities

Table 3: Dose Modification and Management of Hematologic Adverse Events (CRLX101)

Cycle Day	Grade or count (cells/mm  )	Dose Delay or Reduction for Hematological Toxicity (Phase 2 stage and after Cycle 1 of a new dose level in lead-in stage)				
Neutrop	enia					
1 or 15	Grade 2 (<1500)	
 
For first neutropenic eventa, delay CRLX101 dose until ≤ Grade 1, resume CRLX101 with no dose change
 
				
		• For second neutropenic event a , delay CRLX101 until ≤ Grade 1, resume CRLX101 with no dose change, add G-CSF b support				
		
 
For third neutropenic eventa, delay dose until ≤ Grade 1, resume CRLX101 with the dose reduced by one dose level, continue G- CSFb support
 
				
	$\geq$ Grade 3 (<1000)	
 
For first neutropenic eventa, delay CRLX101 dose until ≤ Grade 1, resume CRLX101 with no dose change, add G-CSFb support
 
				
		• For second neutropenic event a , delay CRLX101 until ≤ Grade 1, resume CRLX101 with dose reduced by one dose level, continue G-CSF b support				
		• For third neutropenic event a , delay dose until ≤ Grade 1, resume CRLX101 with the dose reduced by one further dose level, continue G-CSF b support				
Thromb	ocytopenia					
1 or 15	<100,000	• Delay CRLX101 dose until $\geq$ 100,000				

Cycle Day	Grade or count (cells/mm  )	Dose Delay or Reduction for Hematological Toxicity (Phase 2 stage and after Cycle 1 of a new dose level in lead-in stage)							
		• Resume CRLX101 with no dose change							
	Grade 2 (<75,000) and Grade 3 (<50,000)	
 
Delay dose forCRLX101 until ≥ 100,000
 
Resume CRLX101 with no dose change (the dose may be reduced one dose level or kept at the same dose at the discretion of the Principal Investigator or designee)
 
							
		
 
if grade 2 or grade 3 recurs,
 
Hold dose for CRLX101 until ≥ 100,000
 
Resume CRLX101 with dose reduced by one dose level
 
							
	Grade 4	
 
Hold dose for CRLX101 until ≥ 100,000
 
Resume CRLX101 with dose reduced by one dose level
 
Do not make up missing dose
 
							
Anemia									

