1 or 15	≥ Grade 3 (<8g/dL)	
 
Delay dose for CRLX101, and consider RBC transfusion(s) based on clinical criteria
 
After improved to ≤ Grade 2, resume CRLX101 with no dose change (the dose may be reduced one dose level or kept at the same dose at the discretion of the Principal Investigator or designee)
 
Consider EPO support per guidelines
 
If Grade 3 recurs,
 
Delay dose for CRLX101, and consider RBC transfusion(s) based on clinical criteria
 
After improved to ≤ Grade 2, resume CRLX101 with dose reduced by one dose level
 
Consider EPO support per guidelines
 
							

Cycle Day	Grade or count (cells/mm  )	Dose Delay or Reduction for Hematological Toxicity (Phase 2 stage and after Cycle 1 of a new dose level in lead-in stage)
	Grade 4	• Delay dose for CRLX101, and consider RBC transfusion(s) based on clinical criteria
		• After improved to ≤ Grade 2, resume CRLX101 with dose reduced by one dose level
		• Consider EPO support per guidelines.

a A neutropenic event is defined as  $\geq$  Grade 2 neutropenia on D1 or  $\geq$  Grade 3 neutropenia on Day 15

b G-CSF (filgrastim or equivalent, pegfilgrastim is also permitted) should not start until at least 24 hours after discontinuation of chemotherapy. Discontinue G-CSF once ANC is  $\geq$ 1000/mm^3. Wait at least 24 hours after G-CSF is discontinued before resuming chemotherapy.

- Treatment may be delayed for a maximum of 28 days after holding the treatment for toxicities that develop and do not resolve as defined above (exemptions: lymphopenia, or leukopenia in the absence of grade 3 or higher neutropenia).
- Bi-weekly blood counts will be obtained throughout the study. If any evaluation demonstrates grade ≥ 3 neutropenia or grade ≥ 2 thrombocytopenia, a repeat hematology assessment will be obtained 2-4 days later.
- Management of prolonged hematological toxicities while on study treatment

If a participant develops prolonged hematological toxicity such as:

- ≥2 week interruption/delay in study treatment due to CTC grade 3 or worse anemia and/or development of blood transfusion dependence
- ≥3 week interruption/delay in study treatment due to CTC grade 3 or worse neutropenia (ANC < 1 x 109/L)
- $\geq$ 3 week interruption/delay in study treatment due to CTC grade 3 or worse thrombocytopenia (Platelets < 50 x 109/L)

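### Section 3.1.1 raises lead-in participants to 15 mg/m² at Cycle 3 without requiring that 12 mg/m² was tolerated, so a DLT that led to no dose reduction is followed by a 25% higher dose

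*Combined protocol and SAP*

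**What the plan says.** **Dose schedule (Précis, Design; 3.1.1).** CRLX101 is given at 12 mg/m² on Days 1 and 15 of Cycles 1 and 2. Then: "On Cycle 3 Day 1 (C3D1), and Cycle 3 Day 15 (C3D15), CRLX101 will be administered at the previously established MTD", 15 mg/m². The Précis gives the same step, also without a condition. DLTs are assessed on Days 1 to 56 for 12 mg/m² and on Days 57 to 84 for 15 mg/m². Individual tolerance enters afterwards: "Following the DLT assessment period (at the start of Cycle 4), each participant will continue to receive CRLX101" at that participant's own maximum tolerated dose. Apart from one unclear 9 mg/m² provision after two DLTs at 12 mg/m², the decision rules set the dose of additional or later participants.

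**No-increase rule (3.3.1).** "Once a participant has a dose reduction for toxicity, the dose will not be increased".

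**Table 3 (3.3.2.2).** After a first neutropenic event of grade 3 or higher, treatment waits for recovery to grade 1 or better, then: "resume CRLX101 with no dose change, add G-CSF". After a first grade 2 or 3 thrombocytopenia, "the dose may be reduced one dose level or kept at the same dose". Footnote a restricts the trigger: "A neutropenic event is defined as" grade 2 or worse on Day 1, or grade 3 or worse on Day 15. In the lead-in the table applies only "after Cycle 1 of a new dose level in lead-in stage".

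**Table 4 (3.3.2.3).** After a non-hematologic toxicity of grade 3 or higher has resolved to grade 1, CRLX101 *may* be restarted one level lower. Readily corrected laboratory abnormalities need no reduction.

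**DLT definition (3.1.1.1).** It includes febrile neutropenia, "any grade 3-4 thrombocytopenia complicated with hemorrhage", and most grade 3-4 non-hematologic toxicities.

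**The concern.** The lead-in exists to find out whether the combination is tolerable before 15 mg/m² is adopted. DLTs at 12 mg/m² are counted over 56 days, but the text does not link the result to the dose that the same participant receives on Day 57. The cohort rules determine what happens to other participants, while the affected participant's own Cycle 3 dose follows from a fixed schedule.

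At stake is individual safety: someone who has just met the protocol's definition of dose-limiting toxicity could be given more drug at the next infusion because the schedule says so. The two-stage efficacy design is not affected.

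**Working it through.** **1. Size of the step.** 15/12 − 1 = 0.25, a 25% increase.

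**2. Timing.** With 28-day cycles, 2 × 28 = 56 and 3 × 28 = 84, which agrees with the DLT windows in 3.1.1. C2D15 is Day 28 + 15 = 43 and C3D1 is Day 57, so the last interval before the step is 14 days.

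**3. Who is not affected.**
- Participants without a DLT at 12 mg/m²: for them this is planned escalation.
- Participants already reduced (12 to 9 mg/m² under Table 2): 3.3.1 bars any increase. This covers grade 4 thrombocytopenia or anemia managed under Table 3, which requires a reduction.

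**4. Who is affected.** The remaining group had a DLT at 12 mg/m² that led to no reduction, so 3.3.1 is not triggered.
- *Febrile neutropenia that begins after C2D15 and has recovered by C3D1.* It is a DLT under 3.1.1.1. It was not present at the required grade on a Day 1 or Day 15, so footnote a does not count it and Table 3 asks for nothing. The next scheduled dose is 15 mg/m². This is the clearest route.
- *Resolved grade 3-4 non-hematologic DLT.* Table 4 says that the restart *may* be one level lower. If no reduction is made, the C3D1 step applies. The wording can also be read as permission to restart, with the lower level then obligatory; on that reading the participant is protected. The exemption for readily corrected laboratory abnormalities is explicit.
- *Hematologic DLT still present at C3D1.* Table 3's instruction to resume unchanged, or its option to keep the dose, points to 12 mg/m². Section 3.1.1 prescribes 15 mg/m². The two conflict, and neither is given precedence.
- *Hematologic DLT earlier in the lead-in.* A first neutropenic event found at C2D1 or C2D15 is resumed at 12 mg/m². For Cycle 1, Table 3 by its heading gives no rule, and Cycle 2 follows at 12 mg/m². In both cases the step comes at C3D1, after further treatment at 12 mg/m².

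**5. Frequency.** The documents give no DLT rate for 12 mg/m² every 2 weeks with enzalutamide. If a per-participant rate p is assumed, the chance of at least one DLT at 12 mg/m² among n participants is 1 − (1 − p)^n:
- p = 5%: 1 − 0.95³ = 14.3% for n = 3; 1 − 0.95⁶ = 26.5% for n = 6.
- p = 10%: 1 − 0.90³ = 27.1% for n = 3; 1 − 0.90⁶ = 46.9% for n = 6.

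Given the assumed p, these are ceilings for the affected group, because many DLTs lead to a reduction.

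**The case against.** The strongest reply is that a condition may already exist where it cannot be seen. Figure 6 is titled as the lead-in schema and DLT assessment, and a second figure follows the decision rules. Neither could be read in the text available, and either could show a check before C3D1. This stands, so the point concerns the written text only.

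Second, a reader might infer that Table 3 itself sends a participant with ongoing febrile neutropenia or bleeding thrombocytopenia to 15 mg/m², or that a Cycle 1 DLT is followed at once by a raise. The documents do not support either. Section 3.3.2.1 ties dose modification to the level at which the event occurred, Table 3 then points to 12 mg/m², and Cycle 2 stays at 12 mg/m².

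Third, there are safeguards. The monotherapy MTD is 15 mg/m² every 2 weeks (1.2.5.4). Growth factors are allowed during and after a hold, and the bar on prophylaxis can be lifted once neutropenia is identified as a DLT (3.3.2.2.1). The team meets weekly, the principal investigator reviews each participant (7.4.1), and the investigator may stop therapy (3.6.1). These make it possible to avoid the raise but do not require it. The escalation sentence in 7.4.1 refers to toxicity in prior participants, not in the participant about to be dosed.

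**Conclusion.** The point holds on the text of 3.1.1 and the Précis. A participant whose DLT at 12 mg/m² led to no reduction is directed to a 25% higher dose at C3D1. This is clearest for febrile neutropenia arising and recovering between C2D15 and C3D1. It also applies to a resolved grade 3-4 non-hematologic DLT if Table 4's wording is taken as optional. For hematologic events still present at C3D1, the finding is a conflict between two instructions.

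The number affected is small and cannot be estimated. A reader might take 14% to 47% as the expected frequency, but those figures rest on an assumed DLT rate and count every DLT at 12 mg/m². Nor does the 2 of 97 with grade 3 or higher neutropenia in the Phase 2 NSCLC study (1.2.5.7.1) supply a rate: it was seen at 15 mg/m², without enzalutamide, and is not limited to febrile events.

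The conclusion assumes that the figures in 3.1.1 show no condition. If they do show one, the text still needs to state it. The correction is worth making because the consequence falls on an individual participant and the remedy costs almost nothing.

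**What to change.** Add to 3.1.1: *The C3D1 step to 15 mg/m² is given only to participants who had no DLT and no dose reduction at 12 mg/m² in Cycles 1-2; all others stay at 12 mg/m² or at their reduced dose under 3.3.* Make the figures in 3.1.1 match. This also settles the conflict with Table 3 for a DLT still present at C3D1.

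No replacement rule is needed, and DLTs at 12 mg/m² already count in the Day 1 to 84 decision rules. There are no added procedures.

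The downside is possibly one fewer participant observed at 15 mg/m². If one participant has a DLT at 12 mg/m² and the lead-in goes to 6, at most 5 reach 15 mg/m². With no DLT among them, the one-sided 95% upper limit for the DLT rate, 1 − 0.05^(1/n), is 1 − 0.05^(1/5) = 45.1%, instead of 1 − 0.05^(1/6) = 39.3% for 0 of 6. That is a modest loss of precision in a cohort that is already small.
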